Appendix 3. GSI Grading Scale for Severity of Adverse Events and Laboratory Abnormalities

Antiviral Toxicity Grading Scale Version: 01 April 2015

HEMATOLOGY				
	Grade 1	Grade 2	Grade 3	Grade 4
Hemoglobin HIV POSITIVE Adult and Pediatric ≥ 57 Days	8.5 to 10.0 g/dL 85 to 100 g/L	7.5 to < 8.5 g/dL 75 to < 85 g/L	6.5 to < 7.5 g/dL 65 to < 75 g/L	< 6.5 g/dL < 65 g/L
HIV NEGATIVE Adult and Pediatric ≥ 57 Days	10.0 to 10.9 g/dL 100 to 109 g/L OR Any decrease from Baseline 2.5 to < 3.5 g/dL 25 to < 35 g/L	9.0 to < 10.0 g/dL 90 to < 100 g/L OR Any decrease from Baseline 3.5 to < 4.5 g/dL 35 to < 45 g/L	7.0 to < 9.0 g/dL 70 to < 90 g/L OR Any decrease from Baseline ≥ 4.5 g/dL ≥ 45 g/L	< 7.0 g/dL < 70 g/L
Infant, 36–56 Days (HIV POSITIVE OR NEGATIVE)	8.5 to 9.4 g/dL 85 to 94 g/L	7.0 to < 8.5 g/dL 70 to < 85 g/L	6.0 to < 7.0 g/dL 60 to < 70 g/L	< 6.0 g/dL < 60 g/L
Infant, 22–35 Days (HIV POSITIVE OR NEGATIVE)	9.5 to 10.5 g/dL 95 to 105 g/L	8.0 to < 9.5 g/dL 80 to < 95 g/L	7.0 to < 8.0 g/dL 70 to < 80 g/L	< 7.0 g/dL < 70 g/L
Infant, 1–21 Days (HIV POSITIVE OR NEGATIVE)	12.0 to 13.0 g/dL 120 to 130 g/L	10.0 to < 12.0 g/dL 100 to < 120 g/L	9.0 to < 10.0 g/dL 90 to < 100 g/L	< 9.0 g/dL < 90 g/L
Absolute Neutrophil Count (ANC) Adult and Pediatric, ≥ 7 Months[#]	1000 to 1300/mm ³ 1.00 to 1.30 GI/L	750 to < 1000/mm ³ 0.75 to < 1.00 GI/L	500 to < 750/mm ³ 0.50 to < 0.75 GI/L	< 500/mm ³ < 0.50 GI/L
Absolute CD4+ Count HIV NEGATIVE ONLY Adult and Pediatric > 13 Years	300 to 400/mm ³ 300 to 400/μL	200 to < 300/mm ³ 200 to < 300/μL	100 to < 200/mm ³ 100 to < 200/μL	< 100/mm ³ < 100/μL

HEMATOLOGY				
	Grade 1	Grade 2	Grade 3	Grade 4
Absolute Lymphocyte Count HIV NEGATIVE ONLY Adult and Pediatric > 13 Years	600 to 650/mm ³ 0.60 to 0.65 GI/L	500 to < 600/mm ³ 0.50 to < 0.60 GI/L	350 to < 500/mm ³ 0.35 to < 0.50 GI/L	< 350/mm ³ < 0.35 GI/L
Platelets	100,000 to < 125,000/mm ³ 100 to < 125 GI/L	50,000 to < 100,000/mm ³ 50 to < 100 GI/L	25,000 to < 50,000/mm ³ 25 to < 50 GI/L	< 25,000/mm ³ < 25 GI/L
WBCs	2000/mm ³ to 2500/mm ³ 2.00 GI/L to 2.50 GI/L	1,500 to < 2,000/mm ³ 1.50 to < 2.00 GI/L	1000 to < 1,500/mm ³ 1.00 to < 1.50 GI/L	< 1000/mm ³ < 1.00 GI/L
Hypofibrinogenemia	100 to 200 mg/dL 1.00 to 2.00 g/L	75 to < 100 mg/dL 0.75 to < 1.00 g/L	50 to < 75 mg/dL 0.50 to < 0.75 g/L	< 50 mg/dL < 0.50 g/L
Hyperfibrinogenemia	> ULN to 600 mg/dL > ULN to 6.0 g/L	> 600 mg/dL > 6.0 g/L	— —	— —

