Hypouricemia Adult and Pediatric ≥ 1 year Infant < 1 Year	1.5 mg/dL to < LLN 87 μmol/L to < LLN N/A	1.0 to < 1.5 mg/dL 57 to < 87 μmol/L 1.0 mg/dl to < LLN- 57 μmol to < LLN	0.5 to < 1.0 mg/dL 27 to < 57 μmol/L 0.5 to < 1.0 mg/dL 27 to < 57 μmol/L	< 0.5 mg/dL < 27 μmol/L < 0.5 mg/dL < 27 μmol/L
Creatinine**	> 1.50 to 2.00 mg/dL > 133 to 177 μmol/L	> 2.00 to 3.00 mg/dL > 177 to 265 μmol/L	> 3.00 to 6.00 mg/dL > 265 to 530 μmol/L	> 6.00 mg/dL > 530 μmol/L

CHEMISTRY				
	Grade 1	Grade 2	Grade 3	Grade 4
Bicarbonate Adult and Pediatric ≥ 4 Years Pediatric < 4 Years	16.0 mEq/L to < LLN 16.0 mmol/L to < LLN NA	11.0 to < 16.0 mEq/L 11.0 to < 16.0 mmol/L 11.0 mEq/L to <LLN 11.0 mmol/L to <LLN	8.0 to < 11.0 mEq/L 8.0 to < 11.0 mmol/L 8.0 to < 11.0 mEq/L 8.0 to < 11.0 mmol/L	< 8.0 mEq/L < 8.0 mmol/L < 8.0 mEq/L < 8.0 mmol/L
Triglycerides (Fasting)	NA	500 to 750 mg/dL 5.64–8.47 mmol/L	> 750 to 1200 mg/dL > 8.47–13.55 mmol/L	> 1200 mg/dL > 13.55 mmol/L
LDL (Fasting) Adult	130 to 160 mg/dL 3.35 to 4.15 mmol/L	>160 to 190 mg/dL >4.15 to 4.92 mmol/L	> 190 mg/dL >4.92 mmol/L	NA
LDL (Fasting) Pediatric >2 to <18 years	110 to 130 mg/dL 2.84 to 3.37 mmol/L	>130 to 190 mg/dL >3.37 to 4.92 mmol/L	> 190 mg/dL >4.92 mmol/L	NA
Hypercholesterolemia (Fasting) Pediatric < 18 Years	200 to 239 mg/dL 5.16 to 6.19 mmol/L 170 to 199 mg/dL 4.39 to 5.15 mmol/L	> 239 to 300 mg/dL > 6.19 to 7.77 mmol/L > 199 to 300 mg/dL > 5.15 to 7.77 mmol/L	> 300 mg/dL > 7.77 mmol/L > 300 mg/dL > 7.77 mmol/L	NA NA
Creatine Kinase	3.0 to < 6.0 × ULN	6.0 to < 10.0 × ULN	10.0 to < 20.0 × ULN	≥ 20.0 × ULN

* Calcium should be corrected for albumin if albumin is < 4.0 g/dL

** An overlap between the Grade 1 scale and the Lab's normal range for creatinine may result for Male subjects >70 yrs. Please follow the Gilead convention of grading any result within the LLN and ULN a 0.

ENZYMES				
	Grade 1	Grade 2	Grade 3	Grade 4
AST (SGOT)	1.25 to 2.50 × ULN	> 2.50 to 5.00 × ULN	> 5.00 to 10.00 × ULN	> 10.00 × ULN
ALT (SGPT)	1.25 to 2.50 × ULN	> 2.50 to 5.00 × ULN	> 5.00 to 10.00 × ULN	> 10.00 × ULN
GGT	1.25 to 2.50 × ULN	> 2.50 to 5.00 × ULN	> 5.00 to 10.00 × ULN	> 10.00 × ULN
Alkaline Phosphatase	1.25 to 2.50 × ULN	> 2.50 to 5.00 × ULN	> 5.00 to 10.00 × ULN	> 10.00 × ULN
Total Amylase	> 1.0 to 1.5 × ULN	> 1.5 to 2.0 × ULN	> 2.0 to 5.0 × ULN	> 5.0 × ULN
Pancreatic Amylase	> 1.0 to 1.5 × ULN	> 1.5 to 2.0 × ULN	> 2.0 to 5.0 × ULN	> 5.0 × ULN
Lipase	> 1.0 to 1.5 × ULN	> 1.5 to 3.0 × ULN	> 3.0 to 5.0 × ULN	> 5.0 × ULN

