Albumin Pediatrics <16 years	-	2.0 to < LLN g/dL 20 to < LLN g/L	< 2.0 g/dL < 20 g/L	NA
≥ 16 years	3.0 g/dL to < LLN 30 g/L to < LLN	2.0 to < 3.0 g/dL 20 to < 30 g/L	< 2.0 g/dL < 20 g/L	NA

URINALYSIS				
	Grade 1	Grade 2	Grade 3	Grade 4
Hematuria (Dipstick)	1+	2+	3-4+	NA
Hematuria (Quantitative) See Note below				
Females	>ULN - 10 RBC/HPF	> 10-75 RBC/HPF	> 75 RBC/HPF	NA
Males	6-10 RBC/HPF	> 10-75 RBC/HPF	> 75 RBC/HPF	NA
Proteinuria (Dipstick)	1+	2-3+	4+	NA
Proteinuria, 24 Hour Collection				
Adult and Pediatric ≥ 10 Years	200 to 999 mg/24 h	>999 to 1999 mg/24 h	>1999 to 3500 mg/24 h	> 3500 mg/24 h
Pediatric > 3 Mo to < 10 Years	201 to 499 mg/m ² /24 h	>499 to 799 mg/m ² /24 h	>799 to 1000 mg/m ² /24 h	> 1000 mg/ m ² /24 h
Glycosuria (Dipstick)	1+	2-3+	4+	NA

Notes:

- Toxicity grades for Quantitative and Dipstick Hematuria will be assigned by Covance Laboratory, however for other laboratories, toxicity grades will only be assigned to Dipstick Hematuria.
- With the exception of lipid tests, any graded laboratory test with a result that is between the LLN and ULN should be assigned Grade 0.
- If the severity of a clinical AE could fall under either one of two grades (e.g., the severity of an AE could be either Grade 2 or Grade 3), select the higher of the two grades for the AE.

CARDIOVASCULAR				
	Grade 1	Grade 2	Grade 3	Grade 4
Cardiac Arrhythmia (general) (By ECG or physical exam)	Asymptomatic AND No intervention indicated	Asymptomatic AND Non-urgent medical intervention indicated	Symptomatic, non-life-threatening AND Non-urgent medical intervention indicated	Life-threatening arrhythmia OR Urgent intervention indicated
Cardiac-ischemia/Infarction	NA	NA	Symptomatic ischemia (stable angina) OR Testing consistent with ischemia	Unstable angina OR Acute myocardial infarction
Hemorrhage (significant acute blood loss)	NA	Symptomatic AND No transfusion indicated	Symptomatic AND Transfusion of ≤ 2 units packed RBCs (for children ≤ 10 cc/kg) indicated	Life-threatening hypotension OR Transfusion of > 2 units packed RBCs indicated (for children ≤ 10 cc/kg) indicated
Hypertension (with repeat testing at same visit)	140–159 mmHg systolic OR 90–99 mmHg diastolic	> 159–179 mmHg systolic OR > 99–109 mmHg diastolic	> 179 mmHg systolic OR > 109 mmHg diastolic	Life-threatening consequences (eg, malignant hypertension) OR Hospitalization (other than ER visit) indicated

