### **3.6. Data Handling Conventions and Transformations**

By-subject listings will be presented for all subjects in the Safety Analysis Set and sorted by subject ID number, visit date, and time (if applicable) unless otherwise specified. Data collected on log forms, such as AEs, will be presented in chronological order within subject.

Age (in years) on the date of the first dose of study drug and sex at birth will be used for analyses and presentation in listings.

If a subject was not dosed with study drug at all, then the date the informed consent was signed will be used instead of the first dose date of study drug. For some countries, only birth year is collected on the eCRF. In those cases, “01 July” will be used for the unknown birth day and month for the purpose of age calculation, unless age is captured on the eCRF.

Non-PK data that are continuous in nature but are less than the LLOQ or above the upper LOQ will be imputed as follows:

- A value that is one unit less than the limit of quantitation will be used for calculation of descriptive statistics if the datum is reported in the form of “< x” (where x is considered the limit of quantitation). For example, if the values are reported as < 50 and < 5.0, values of 49 and 4.9, respectively, will be used for calculation of summary statistics. An exception for this rule is any value reported < 1. For the values reported as < 1 or < 0.1, value of 0.9 or 0.09 will be used for calculation of summary statistics.
- A value that is one unit above the limit of quantitation will be used for calculation of descriptive statistics if the datum is reported in the form of “> x” (where x is considered the limit of quantitation). Values with decimal points will follow the same logic as above.
- The limit of quantitation will be used for calculation of descriptive statistics if the datum is reported in the form of “≤ x” or “≥ x” (where x is considered the limit of quantitation).

The COBAS® AmpliPrep/COBAS® TaqMan® HCV Test, v2.0 for use with the High Pure System was used to determine HCV RNA results in this study. The LLOQ of the assay is 15 IU/mL.

When the calculated HCV RNA value is within the linear range of the assay, then the result will be reported as the “<< numeric value>> IU/mL”. This result will be referred to in this document as the numeric result or as “≥ LLOQ detected” for categorical result.

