### 5.2. Other Baseline Characteristics

Other baseline characteristics include:

- weight in kg
- height in cm
- body mass index (BMI; in kg/m^2)
- HCV genotype (1 [further broken down to 1a and 1b], 2, 3, 4, 5, 6, or other, as appropriate)
- cirrhosis (presence, absence, not determined)
- IL28B (CC, CT, TT)
- baseline HCV RNA (IU/mL) (< 800,000 IU/mL, ≥ 800,000 IU/mL)
- baseline HCV RNA (log10 IU/mL) as a continuous variable and as categories (< 6 log10 IU/mL, ≥ 6 log10 IU/mL)
- baseline ALT (U/L) as a continuous variable and as categories (≤1.5 × ULN, > 1.5 × ULN)
- estimated glomerular filtration rate (eGFR) using Schwartz Formula (mL/min/1.73m^2)
- prior treatment experience (treatment naïve, treatment experienced)
- most recent response to prior HCV treatment (non-response, relapse/breakthrough, unknown) for treatment experienced subjects

- mode of HCV Infection
- bone age in years
- Tanner Stage

Estimated glomerular filtration rate will be calculated using Schwartz Formula ( $\text{mL}/\text{min}/1.73\text{m}^2$ )  $k \times L/\text{Scr}$  [(k is a proportionality constant, for adolescent females  $\geq 12$  years old is 0.55; for adolescent males  $\geq 12$  years old is 0.70, and for children 3- <12 years old is 0.55); L is height in centimeters (cm); and Scr is serum creatinine (mg/dL)].

These baseline characteristics will be summarized by HCV genotype (1 [further broken down to 1a and 1b], 2, 3, 4, 5, 6, or other, as appropriate, and total) in each age group using descriptive statistics (n, mean, SD, median, Q1, Q3, minimum, and maximum) for continuous variables and using the numbers and percentages of subjects for categorical variables. The summary of baseline characteristics will be provided for the Safety Analysis Set.

A by-subject listing of other baseline characteristics will be provided by subject ID number in ascending order.

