### **7.2.1. Summaries of Numeric Laboratory Results**

Descriptive statistics (n, mean, SD, median, Q1, Q3, minimum, and maximum) will be provided by age group for ALT, aspartate aminotransferase (AST), total bilirubin, alkaline phosphatase, hemoglobin, reticulocytes, white blood cell (WBC), neutrophils, lymphocytes, platelets, and international normalized ratio (INR) as follows:

- Baseline values
- Values at each postbaseline analysis window
- Change from baseline at each postbaseline analysis window

A baseline laboratory value will be defined as the final assessment performed on or prior to the date/time of first dose of study drug. Change from baseline to a postbaseline visit will be defined as the visit value minus the baseline value. The mean, median, Q1, Q3, minimum, and maximum will be displayed to the reported number of digits; SD to the reported number of digits plus 1.

Median (Q1, Q3) of the observed values for these laboratory parameters will be plotted using a line plot by visit.

In the case of multiple values in an analysis window, data will be selected for analysis as described in Section 3.7.3 (Selection of Data in the Event of Multiple Records in a Window).

The number of subjects with hemoglobin < 10 g/dL and < 8.5 g/dL at any postbaseline visits (up to 30 days after the last dose of any study drug) will be summarized.

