### **7.2.2. Graded Laboratory Values**

The Gilead Grading Scale for Severity of Adverse Events and Laboratory Abnormalities will be used for assigning toxicity grades to laboratory results for analysis as Grade 0, Grade 1, Grade 2, Grade 3, or Grade 4. Grade 0 includes all values that do not meet the criteria for an abnormality of at least Grade 1. Some laboratory tests have criteria for both increased and decreased levels; analyses for each direction (ie, increased, decreased) will be presented separately.

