#### 7.2.2.2. Summaries of Laboratory Abnormalities

Laboratory data that are categorical will be summarized using the number and percentage of subjects in the study with the given response at baseline and each scheduled postbaseline visit.

The following summaries (number and percentage of subjects) for treatment-emergent laboratory abnormalities will be provided by analyte in each age group; subjects will be categorized according to the most severe postbaseline abnormality grade for a given analyte:

- Graded laboratory abnormalities
- Grade 3 or above laboratory abnormalities

For all summaries of laboratory abnormalities, the denominator is the number of subjects with nonmissing postbaseline values up to 30 days after last dose for the laboratory parameter of interest.

A by-subject listing of treatment-emergent Grade 3 or above laboratory abnormalities will be provided by subject ID number and visit in chronological order. This listing will include all test results that were collected throughout the study for the analyte of interest, with all applicable severity grades or abnormal flags displayed.

For subjects with at least one event of treatment-emergent Grade 3 or above laboratory abnormality of creatine kinase (CK) or lipase, a listing of AEs will be provided.

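### The SAP's only summary tables of on-treatment creatinine use one absolute grading row for all ages, so a zero count in the youngest group is weak evidence of no change

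*Protocol*

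**What the plan says.** Protocol Appendix 3 (Chemistry) grades creatinine on a single row in absolute units. Grade 1 is "> 1.50 to 2.00 mg/dL" and Grade 3 starts above 3.00 mg/dL. The row has no paediatric band, no multiple of the upper limit of normal (ULN) and no change-from-baseline criterion. Its only age footnote concerns men over 70.

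Other rows for tests on this study's panel do adapt. Haemoglobin has a baseline-relative criterion ("Any decrease from Baseline 2.5 to < 3.5 g/dL" for Grade 1), albumin has a paediatric band ("Albumin Pediatrics <16 years"), and ALT, AST, lipase and creatine kinase use ULN multiples.

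SAP 7.2.2 applies this scale and states that "Grade 0 includes all values that do not meet the criteria for an abnormality of at least Grade 1". SAP 7.2.2.1 requires a rise of at least one grade for an abnormality to be treatment-emergent. SAP 7.2.2.2 plans two summaries by age group, all grades and Grade 3 or above, in which "subjects will be categorized according to the most severe postbaseline abnormality grade for a given analyte".

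The by-visit numeric summaries in SAP 7.2.1 cover ALT, AST, total bilirubin, alkaline phosphatase and "hemoglobin, reticulocytes, white blood cell (WBC), neutrophils, lymphocytes, platelets, and international normalized ratio (INR) as follows". Creatinine is not on that list. eGFR appears in SAP 5.2 only as a baseline characteristic; the Schwartz constant "for children 3- <12 years old is 0.55" is given there.

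**The concern.** Creatinine at a given eGFR depends on body size, so a fixed line at 1.50 mg/dL stands for a much larger relative change in a small child than in a tall adolescent. The graded tables have one column per age group, and a reader will compare the columns. If the youngest column shows no graded creatinine abnormality, the natural reading is that creatinine did not change there. The scale cannot support that reading, and no by-visit value or change from baseline is planned that would.

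Safety and tolerability is the primary objective of the Treatment Phase (Protocol 2). The protocol also makes renal function relevant to exposure: GS-331007 is eliminated renally, and its expected exposure at ages 3 to <6 years was scaled on renal capacity (Protocol 1.3).

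**Working it through.** The documents give no figure for the change in eGFR at a grade line, so there is none to reproduce.

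**Inputs**
- Schwartz formula: eGFR = k × L / Scr, with L in cm and Scr in mg/dL (SAP 5.2, Protocol 6.10.10).
- k = 0.55 for ages 3 to <12 (SAP 5.2 only). For ages 12 and over, k = 0.55 for females and 0.70 for males (both documents).
- Entry eGFR of 90 mL/min/1.73 m², the lowest value allowed at screening (Protocol 4.3, criterion 3g). An entry value of 120 is an added assumption.
- Highest Grade 0 creatinine: 1.50 mg/dL. Highest value below Grade 3: 3.00 mg/dL.
- Heights are assumptions, because the documents give no height data. Height is held at its baseline value.

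**Formulas**
- Creatinine at entry = k × L / entry eGFR.
- eGFR at the Grade 1 line = k × L / 1.50.
- Loss = 1 − (eGFR at the line) / (entry eGFR). For entry at 90 this is 1 − k × L / 135.
- Fold rise to the line = 1.50 / (creatinine at entry).

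**Worked case.** At 90 cm with entry at 90, creatinine at entry is 0.55 × 90 / 90 = 0.550 mg/dL. eGFR at 1.50 mg/dL is 0.55 × 90 / 1.50 = 33.0. The loss is 1 − 33.0 / 90 = 63.3%, and the fold rise is 1.50 / 0.550 = 2.73.

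**Results at the Grade 1 line, k = 0.55**

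| Height (cm) | Creatinine at eGFR 90 (mg/dL) | eGFR at 1.50 mg/dL | Loss, entry 90 | Loss, entry 120 | Fold rise, entry 90 |
|---|---|---|---|---|---|
| 90 | 0.550 | 33.0 | 63.3% | 72.5% | 2.73 |
| 100 | 0.611 | 36.7 | 59.3% | 69.4% | 2.45 |
| 110 | 0.672 | 40.3 | 55.2% | 66.4% | 2.23 |
| 120 | 0.733 | 44.0 | 51.1% | 63.3% | 2.05 |
| 130 | 0.794 | 47.7 | 47.0% | 60.3% | 1.89 |
| 150 | 0.917 | 55.0 | 38.9% | 54.2% | 1.64 |

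**Adolescents at the Grade 1 line, entry 90**
- Female, k = 0.55: eGFR 55.0 at 150 cm (38.9% loss) and 58.7 at 160 cm (34.8% loss).
- Male, k = 0.70: eGFR 70.0 at 150 cm (22.2% loss) and 79.3 at 170 cm (11.9% loss).

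**Grade 3 line, k = 0.55, entry 90.** At 90, 100, 110 and 120 cm, eGFR at 3.00 mg/dL is 16.5, 18.3, 20.2 and 22.0. The losses are 81.7%, 79.6%, 77.6% and 75.6%. The Grade 3 or above summary is therefore less sensitive still.

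**Search for another SAP summary table.** SAP 7.2.2.3 covers liver tests only. The sentence on categorical laboratory data in SAP 7.2.2.2 does not reach a numeric analyte. The Appendix 3 convention of grading any in-range result as 0 can only lower a grade.

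**The case against.** The strongest reply is that this asks for extra tables and exposes no error. Protocol 8.5.3 promises numeric summaries of selected laboratory data only, and SAP 7.2.1 makes a selection. The scale is the sponsor's general antiviral scale, used unchanged. Creatinine is not its only single absolute row: platelets and white cells have one too. All of this stands, and no contradiction between the documents is claimed.

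The second reply is that a consequential rise would still be seen.
- By-subject listings flag out-of-range values whatever their grade (SAP 7.2).
- Laboratory abnormalities that need intervention, or that lead to interruption, modification or discontinuation of study drug, must be recorded as adverse events (Protocol 7.1.3). They then enter the adverse event tables by age group (SAP 7.1.6).
- The data monitoring committee reviews safety data about every 6 months (Protocol 8.7), under a charter that is not available here.

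A reader might infer from the arithmetic that a serious decline in a small child would go unnoticed. These routes mean the documents do not support that. What they do not supply is a planned SAP summary table with counts and denominators for asymptomatic creatinine change.

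The third reply concerns relevance. The Treatment Phase primary endpoint is adverse events (Protocol 8.1.2), so graded creatinine is supportive. Scaling exposure on renal capacity says how the kidney affects the drug and nothing about the reverse. The protocol describes GS-331007 as inactive and reports no clinically significant exposure-safety relationship across a broad range of its exposure (Protocol 8.6). A reader might infer a suspected renal effect; the documents give no ground for one.

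Lastly, the age contrast is not clean. At 150 cm a child and an adolescent female have the same 39% loss, and the adolescent examples alone run from 12% to 39%. That stands, and it confines the contrast mainly to shorter children.

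**Conclusion.** The point holds as a minor weakness in the analysis plan. Within the SAP, the two graded summaries are the only planned summary tables of on-treatment creatinine. For an assumed child of 90 to 120 cm entering at eGFR 90, they count a loss of about 63% to 51% as Grade 0. The same line is reached at a 39% loss at 150 cm with k = 0.55, and at about 12% for a 170 cm male with k = 0.70. A higher entry eGFR widens the unseen loss: 73% to 63% at 90 to 120 cm from an entry value of 120. A zero count in the youngest column is therefore weak evidence of no creatinine change, and it is not comparable with a zero in a column of taller subjects.

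This rests on assumed heights held at baseline, so no number of affected subjects can be given. It also assumes that k = 0.55 was used at screening below age 12, because Protocol 6.10.10 gives k only for ages 12 and over. The finding about tables covers the SAP alone and does not extend to what the data monitoring committee receives.

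**What to change.** Add serum creatinine and Schwartz eGFR to SAP 7.2.1, as value and change from baseline by visit and age group. Take k by sex and by age at first dose, using the SAP 5.2 constants. SAP 3.6 already sets that convention: "Age (in years) on the date of the first dose of study drug and sex at birth will be used for analyses". Keep both graded tables as they are.

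Optionally, add one descriptive table by age group of each subject's maximum postbaseline-to-baseline creatinine ratio, in categories prespecified by the sponsor. The lowest category should start below 1.64-fold. That is the smallest rise that reaches Grade 1 among the child heights considered (150 cm, entry eGFR 90), so the table would add information at each of those heights. A higher first cut would not: 2.5-fold, for instance, lies above the Grade 1 line for every child height considered from 100 cm upwards.

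The cost is SAP text and one or two descriptive outputs. Creatinine is already in the chemistry panel (Protocol 6.10.1) and height is measured at each visit (Protocol 6.10.5), so no new procedure is needed. The downside is that small fluctuations in low creatinine values will be counted.

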3.6. Discontinuation Criteria

The Medical Monitor should be consulted prior to subject discontinuation when medically feasible. Study medication must be discontinued in the following instances:

- Intercurrent illness that would, in the judgment of the investigator, affect assessments of clinical status to a significant degree. Following resolution of intercurrent illness, the subject may resume study dosing at the discretion of the investigator
- Unacceptable toxicity (as defined in Section 7 of the protocol) or toxicity that, in the judgment of the investigator, compromises the ability to continue study-specific procedures or is considered to not be in the subject's best interest.
- Subject noncompliance

- Pregnancy of female subject or female partner of male subject.
- Efficacy failure as defined in Section 3.5.
- Significant protocol violation that impacts subject safety
- Subject request to discontinue for any reason; it is important to determine whether the withdrawal of consent is primarily due to an AE, lack of efficacy, or other reason.
- Discontinuation of the study at the request of Gilead, regulatory agency, or an Institutional Review Board (IRB)/Independent Ethics Committee (IEC).

Subjects who meet any of the following criteria must stop treatment with SOF/VEL FDC:

- Elevation of ALT and/or AST above the upper limit of normal and $> 5x$ Day 1 or nadir, confirmed by immediate repeat testing
- Elevation of ALT $>15x$ ULN, confirmed by immediate repeat testing
- Elevation of ALT $>3x$ Day 1 and total bilirubin $>2x$ ULN, confirmed by immediate repeat testing
- Any Grade 3 or greater rash associated with constitutional symptoms
- Any Grade 4 adverse event assessed as related to administration of SOF/VEL FDC

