5.2. Dosage and Administration of SOF/VEL FDC

Subjects 12 to < 18 years old enrolled in the PK Lead-in Cohort 1 or in the Treatment Phase

SOF/VEL FDC 400/100 mg tablets will be administered once daily with or without food. Subjects determined unable to swallow the placebo to match the 400/100 mg SOF/VEL FDC tablet will be re-assigned to 2 x 200/50 mg SOF/VEL FDC tablets daily. Subjects unable to swallow the reduced strength SOF/VEL FDC 200/50 mg tablets will be reassigned to SOF/VEL FDC oral granule formulation (8 x 50/12.5 mg packets).

Subjects 6 to < 12 years old enrolled in the PK Lead-in Cohort 2 or in the Treatment Phase

SOF/VEL FDC 200/50 mg tablets will be administered once daily with or without food. Subjects determined unable to swallow the placebo tablet 200/50 mg SOF/VEL FDC will be reassigned to SOF/VEL FDC oral granule formulation (4 x 50/12.5 mg packets).

Subjects 3 to < 6 years old enrolled in the PK Lead-in Cohort 3 or in the Treatment Phase

SOF/VEL FDC 50/12.5 mg oral granules in a packet will be administered once daily with or without food. Subjects who weigh ≥ 17 kgs will be assigned to 200/50 mg SOF/VEL FDC oral granules (4 x 50/12.5 mg packets) and subjects who weigh < 17 kgs will be assigned to 150/37.5 mg SOF/VEL FDC oral granules (3 x 50/12.5 mg packets). The instructions dosing of oral granules are defined in Section 5.2.1.

Subjects should be instructed that if vomiting occurs within 3 hours of dosing an additional tablet or granules packets should be taken according to the dosing instructions above. If vomiting occurs more than 3 hours after dosing, no replacement dose is required that day.

If a dose is missed and it is within 18 hours of the normal regular scheduled time, subjects should be instructed to take the tablet or granules as soon as possible and then follow with the next dose at the usual scheduled time.

If it is after 18 hours then it is considered a missed dose. Subjects should be instructed to take the next dose at the usual next scheduled time. Subjects should be instructed not to take a double dose.

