7.2.2. Assessment of Severity

The severity grading of AEs will be assessed as Grade 1, 2, 3, or 4 using the GSI Grading Scale for Severity of Adverse Events and Laboratory Abnormalities ([Appendix 3](#)). For AEs associated with laboratory abnormalities, the event should be graded on the basis of the clinical severity in the context of the underlying conditions; this may or may not be in agreement with the grading of the laboratory abnormality.

7.3. Investigator Requirements and Instructions for Reporting Adverse Events and Serious Adverse Events to Gilead

Requirements for collection prior to study drug initiation

After obtaining informed consent, but prior to initiation of study medication, the following types of events should be reported on the case report form (CRF/eCRF): all SAEs and adverse events related to protocol-mandated procedures.

Adverse Events

Following initiation of study medication, collect all AEs, regardless of cause or relationship, until 30 days after last administration of study IMP and report to the CRF/eCRF database as instructed.

All AEs should be followed up until resolution or until the adverse event is stable, if possible. Gilead Sciences may request that certain AEs be followed beyond the protocol-defined follow-up period.

Serious Adverse Events

All SAEs, regardless of cause or relationship, that occur after the subject first consents to participate in the study (ie, signing the informed consent) and throughout the duration of the study, including the protocol-required posttreatment follow-up period, must be reported to the eCRF database and Gilead Pharmacovigilance and Epidemiology (PVE) as instructed. This also includes any SAEs resulting from protocol-associated procedures performed after informed consent is signed.

Investigators are not obligated to actively seek SAEs after the protocol defined follow up period; however, if the investigator learns of any SAEs that occur after study participation has concluded and the event is deemed relevant to the use of IMP, he/she should promptly document and report the event to Gilead PVE.

- All AEs and SAEs will be recorded in the eCRF database within the timelines outlined in the eCRF completion guideline.

Electronic Serious Adverse Event (eSAE) Reporting Process

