Pediatric ≤ 17 Years (with repeat testing at same visit)	NA	91st–94th percentile adjusted for age, height, and gender (systolic and/or diastolic)	≥ 95th percentile adjusted for age, height, and gender (systolic and/or diastolic)	Life-threatening consequences (eg, malignant hypertension) OR Hospitalization indicated (other than emergency room visit)
Hypotension	NA	Symptomatic, corrected with oral fluid replacement	Symptomatic, IV fluids indicated	Shock requiring use of vasopressors or mechanical assistance to maintain blood pressure
Pericardial Effusion	Asymptomatic, small effusion requiring no intervention	Asymptomatic, moderate or larger effusion requiring no intervention	Effusion with non-life-threatening physiologic consequences OR Effusion with nonurgent intervention indicated	Life-threatening consequences (eg, tamponade) OR Urgent intervention indicated

CARDIOVASCULAR				
	Grade 1	Grade 2	Grade 3	Grade 4
Prolonged PR Interval	PR interval 0.21 to 0.25 sec	PR interval > 0.25 sec	Type II 2nd degree AV block OR Ventricular pause > 3.0 sec	Complete AV block
Pediatric ≤ 16 Years	1st degree AV block (PR > normal for age and rate)	Type I 2nd degree AV block	Type II 2nd degree AV block	Complete AV block
Prolonged QTc	Asymptomatic, QTc interval 0.45 to 0.47 sec OR Increase interval < 0.03 sec above baseline	Asymptomatic, QTc interval 0.48 to 0.49 sec OR Increase in interval 0.03 to 0.05 sec above baseline	Asymptomatic, QTc interval ≥ 0.50 sec OR Increase in interval ≥ 0.06 sec above baseline	Life-threatening consequences, eg, Torsade de pointes or other associated serious ventricular dysrhythmia
Pediatric ≤ 16 Years	Asymptomatic, QTc interval 0.450 to 0.464 sec	Asymptomatic, QTc interval 0.465 to 0.479 sec	Asymptomatic, QTc interval ≥ 0.480 sec	Life-threatening consequences, eg, Torsade de pointes or other associated serious ventricular dysrhythmia
Thrombosis/Embolism	NA	Deep vein thrombosis AND No intervention indicated (eg, anticoagulation, lysis filter, invasive procedure)	Deep vein thrombosis AND Intervention indicated (eg, anticoagulation, lysis filter, invasive procedure)	Embolic event (eg, pulmonary embolism, life-threatening thrombus)
Vasovagal Episode (associated with a procedure of any kind)	Present without loss of consciousness	Present with transient loss of consciousness	NA	NA

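### In the severity scale, the Grade 4 hemorrhage cell repeats the Grade 3 pediatric limit (≤ 10 cc/kg), so a small transfusion in a child grades as 4 and a larger one meets neither pediatric limit.

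*Protocol*

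**What the plan says.** Protocol Appendix 3, Cardiovascular, has one row for hemorrhage with significant acute blood loss. Grade 1 does not apply, and the other cells are:

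- Grade 2: "Symptomatic AND No transfusion indicated".
- Grade 3: symptomatic, together with "Transfusion of ≤ 2 units packed RBCs (for children ≤ 10 cc/kg) indicated".
- Grade 4: life-threatening hypotension, or "Transfusion of > 2 units packed RBCs indicated (for children ≤ 10 cc/kg) indicated".

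A note in the same appendix covers a clinical AE that could fall under either of two grades: "select the higher of the two grades for the AE".

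Two sections of the protocol body use the result. Section 7.2.2: "The severity grading of AEs will be assessed as Grade 1, 2, 3, or 4 using the GSI Grading Scale". Section 3.6 lists, among the events for which SOF/VEL must be stopped: "Any Grade 4 adverse event assessed as related to administration of SOF/VEL FDC".

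**The concern.** A limit that separates two grades has to change direction between them. The adult limit does; the pediatric one is the same in both cells. For a child without life-threatening hypotension, the smaller transfusion then gets the higher grade and the larger one gets no grade from the pediatric limits.

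This trial enrolls only subjects aged 3 to under 18 years at Day 1 (Section 4.2), so the faulty limit is the one written for its population. The Grade 3/4 boundary also has a consequence. The stopping list in Section 3.6 includes related Grade 4 AEs but has no general rule for Grade 3. Read literally, a related bleed with a small transfusion forces the child off a 12-week course, while a bleed with a larger transfusion triggers nothing through the pediatric limit. A stop forced this way would also count as an AE leading to discontinuation, which is the focus of the Treatment Phase primary endpoint (Section 8.1.2).

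**Working it through.** No sample-size or error-rate figure is involved, and the plan gives no figure to reproduce. The check compares the two cells and applies the scale's own tie-break.

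**Inputs.** From Appendix 3: the pediatric limits for Grade 3 (≤ 10 cc/kg) and Grade 4 (≤ 10 cc/kg), and the higher-grade note. From Protocol Section 5.2, only to supply a realistic weight: the 17 kg dosing cut ("subjects who weigh < 17 kgs will be assigned to 150/37.5 mg SOF/VEL FDC oral granules").

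**Step 1: apply the cells.** Take a symptomatic child for whom transfusion is indicated, without life-threatening hypotension.

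| Volume indicated | Grade 3 pediatric limit | Grade 4 pediatric limit, as printed | Grade as printed | Grade if the Grade 4 limit were > 10 cc/kg |
|---|---|---|---|---|
| ≤ 10 cc/kg | met | met | 4, by the higher-grade note | 3 |
| > 10 cc/kg | not met | not met | none from the pediatric limits | 4 |

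As printed there is an overlap below the limit and a gap above it. With the sign reversed there is neither.

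**Step 2: put a weight in.** The limit at 17 kg is 10 cc/kg × 17 kg = 170 cc. As printed, 170 cc or less is Grade 4. A transfusion of 200 cc is 200 / 17 ≈ 11.8 cc/kg and meets neither pediatric limit. The 17 kg figure is only an illustration; it plays no part in grading.

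**Step 3: follow it into the analysis.** SAP Section 7.1.6 tabulates AEs as Grade 2 or above and Grade 3 or above. A child who needs transfusion cannot be Grade 2, because that cell requires that no transfusion be indicated, so the event is Grade 3 or 4 on any reading. Both kinds of table count it the same way. What can change is the grade shown in listings and whether the Section 3.6 stop applies.

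**Step 4: look for a correction elsewhere.** No other part of the protocol or SAP gives a different pediatric transfusion limit.

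**The case against.** The strongest objection is that everything rests on one symbol in a table extracted from PDF. The same appendix shows damage elsewhere: a garbled word in the infection row, and a calcium row whose label does not fit its limits. A misread sign therefore cannot be excluded, and this objection stands as a caveat. Against it, the other comparison signs in the hemorrhage row read sensibly. The Grade 4 cell also repeats a word, which suggests that the parenthesis was carried over from Grade 3 without being adapted.

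The remaining objections bear on size:

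- The intended limit is easy to infer from the adult split. That is true, but the written tie-break points a literal reader to the wrong grade, and sites may differ.
- A grader could fall back on the adult unit limits, which cover every volume. This is possible, but the row does not say to do so where it gives a separate limit for children.
- Life-threatening hypotension makes the event Grade 4 at any volume, and Section 3.6 also lets the investigator stop treatment on judgment. Both are correct, and they limit the harm from the gap above 10 cc/kg.
- Grading a small transfusion too high errs toward stopping the drug, which is the cautious direction for toxicity. It still imposes a stop that the scale presumably did not intend.

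Together these points show that the consequence is small. None of them makes the two cells consistent.

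**Conclusion.** The Grade 4 pediatric limit is wrong as written, provided that the source PDF shows the same sign. It inverts the order of severity for children, and it does so at the boundary that decides a mandatory stop.

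The effect should be very rare: the child must have a hemorrhage that needs transfusion, and the stopping rule applies only if the event is judged related. The row could apply to about 100 of about 200 subjects if children means 3 to under 12 years, the SAP Section 1.2 usage, or to all of about 200 if it means under 18. Those are the numbers covered by the row, not the numbers expected to be affected. The PK and SVR12 methods do not use the grade, and the tables pooled by grade are unchanged. This is a minor correction, worth making because it is cheap.

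**What to change.** Check the Grade 4 hemorrhage cell against the source PDF. If it reads ≤ 10 cc/kg, change it to > 10 cc/kg so that it complements Grade 3 as the adult limit does, and send the corrected cell to sites. No analysis or SAP text changes.

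The edit is a single sign, but it modifies the protocol, so the IRB/IEC submission and approval described in Sections 9.1.2 and 9.2.1 apply; it could travel with the next amendment. Appendix 3 carries its own version date (01 April 2015), so the sponsor should also correct the parent scale, to keep the two from diverging.
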